Hypothesis 3.1: Veterans in the PHIT group will have higher quality of life [measured by the physical function subscale of the Veterans Rand-12 (VR-12)] & better cognition (measured by SLUMS) & caregivers will have lower caregiver burden (Caregiver Burden Inventory).^{10,11} Assessments will occur at baseline, 60, and 180 days. Veterans in the PHIT group will be more informed and motivated healthcare consumers [measured by the Patient Activation measure (PAM) at baseline and 30 days].

II. Background and Significance:

B.1. Functional decline after acute hospitalization: a hidden epidemic.

Hospitalization is a profound contributor to functional loss and disability in older adults.^{1,2} Considerable evidence exists for hospital-associated deconditioning (HAD),² including dramatic and rapid loss of muscle mass and strength,¹² slower walking speed,¹³ and greater difficulty negotiating activities of daily living following hospital discharge.¹⁴ Therefore, it is not surprising that older adults who are hospitalized are 60 times more likely to develop disability.¹ Comorbidities, the concurrent presence of two or more medically diagnosed diseases, further exacerbate the sequelae associated with hospitalization.¹⁵ This is of particular concern to healthcare professionals serving the Veteran population, as this growing population¹⁶ has a higher prevalence of chronic disease,¹⁷ lower level of physical function⁶ and decreased healthrelated quality of life⁸ compared to their age-matched peers. Furthermore, older adults experience a sharp decline in home and community mobility after hospitalization. On average, scores on the Life-Space Mobility Assessment-a measure designed to capture activity frequency and dependence in the home and community-decrease significantly in older adults after hospitalization and remain below pre-hospitalization levels 2 years later.¹⁸ Despite these significant declines, many of the healthcare efforts for older adults neglect to specifically address functional deficits stemming from hospitalization.^{19,20} Alarmingly, this reduced physical activity and function after hospitalization is also strongly and independently tied to hospital readmission risk.²¹ Thus, it appears that many modifiable risk factors (including impaired gait speed and lower extremity weakness) may persist as portents of poor health, re-hospitalization, or death¹⁴ in older adults following acute hospitalization.

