B.2. Physical function after hospitalization is a powerful biomarker of health for older adults. Although the risk factors for the development of disability are likely to be complex and multifactorial, there is evidence to suggest that physical function alone may be a powerful biomarker of overall health following acute hospitalization.²¹⁻²⁴ In older adults, lower extremity weakness is associated with poor mobility and increased fall risk.²⁵⁻²⁸ Similarly, in the Veteran population, every 0.10 m/s decrease in gait speed during and after an acute hospitalization is associated with increased self-reported disability, decreased physical health, and increased health-care utilization.⁹ These strong associations between physical function and health highlight the need for more intensive interventions which address mobility in older Veterans with HAD. Our preliminary data suggest that mobility is an important modifiable risk factor for poor outcomes in older Veterans with HAD that can be effectively addressed with more intensive rehabilitation strategies.

B.3. Functional decline is associated with increased caregiver burden.

Older Veterans are often cared for by family caregivers,²⁹ and this assistance may be the difference between staying at home and the need for institutionalization. While many variables contribute to the degree of burden a caregiver experiences, one of the strongest predictors of high caregiving burden is the functional ability of the Veteran being cared for.³⁰ A Veteran with low ADL function is likely to require more time and assistance with care, both factors which are related to higher levels of caregiver burden.³¹ When the burden becomes too great for a caregiver, there is potential for increased healthcare costs through either a need for higher volume of home services or eventual institutionalization. Thus, implementing the PHIT program has the potential to improve function and level of independence of the care recipient, while concurrently decreasing the burden on caregivers. Our intervention may impart long-term benefits on both the caregiver and Veteran care recipient by delaying or eliminating the need for institutionalization, or by reducing the amount of intensive support at home in the form of Home Based Primary Care (HBPC) services.

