produced clinically meaningful improvements strongly supporting the importance of treatment strategy, and 2) the benefits of the PHIT intervention continued past the endpoint of the intervention suggesting sustainability (~30 days). In fact, performance in the UC group worsened from 30 to 60 days (after HH physical therapy), while improvements in the PHIT group continued after intervention (30-60 days). Furthermore, though both groups had similar medical complexity, the PHIT group participants had no ER visits or re-hospitalization at 90 days, while 6 episodes (over 2 individuals) were reported in the UC group. Finally, our pilot data included an ethnically diverse group with 23% African American and 5% Hispanic or Latino participants.

[figure not shown]

Figure 2. Phase II Colorado Pilot Study outcomes for SPPB, mPPT, and 4MW (n=18). Intervention was complete, on average, by 31.1 days (PHIT) and 35.3 days (UC). Data reported as mean±SE.

Clinically meaningful improvements can be summarized as follows: A one point difference in the SPPB represents substantial meaningful change,⁴⁶ and we saw differences twice this large in our preliminary data. In fact, PHIT resulted in a 60% improvement in function at 60 days compared to only 9.7% improvement with UC. For walking speed, a 0.1m/s difference in walking speed represents substantial meaningful change,⁴⁶ and we saw differences almost twice this large in our preliminary data. In fact, 30% of patients in the PHIT group achieved >1.0m/s walking speed (threshold for independent community ambulation)⁴⁷ at 60 days; no UC group patients achieved this walking speed. Importantly, both groups received a comparable number of visits. Furthermore, these results provide evidence for the investigative team's experience managing medically complex patients using the proposed intervention strategy with favorable outcomes.

IV. Research Methods

A. Outcome Measure(s): All measures and time points for each to be assessed are summarized in Table 1. Copies of each tool are attached to this application.

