The Life-Space Assessment (LSA) is a self-report measure assessing a patient's movements, extending from within the home to movement beyond a patient's town or geographic region.⁶¹ The life-space assessment is a continuous measure which can be scored from 0 (totally bedbound and dependent with all activity) to 120 (independent with community ambulation without assistance). The scores take into account both the performance of movement within and outside the home, the frequency of the movement, and the amount of assistance required. Specifically, this measure allows evaluation of actual mobility performed in the home and community, and can be evaluated for older adults across all levels of function. LSA has concurrent validity with physical function measures, as well as self-reported health and ADL disability.⁶² The Life-Space Assessment has good test-rest-reliability (ICC=0.96), and is responsive to change in community-dwelling older adults.⁶¹

Quality of Life and Caregiver Burden (Aim 3)

The Veterans RAND 12 Item Health Survey (VR-12) will be used to assess the quality of life in Veterans. The SF-12 has strong concurrent validity with well-established quality of life measures and is reliable for assessing changes in quality of life in community dwelling adults.⁶³

The Caregiver Burden Inventory (CBI) is a multi-dimensional 24-item scale with a five-point scoring system from 0 (never) to 4 (nearly always). The subscales of the CBI demonstrate strong convergent validity with caregiver depression, caregiver satisfaction, and number of caregiver tasks.³¹

Adverse Events Reporting Script will be used to assess any adverse events (e.g. ER visit(s), hospitalization(s), major illness/injury) which occurred since the last study visit and whether the participant is completing their exercises. The AE script will be administered 7 times, once at each of the 5 study visits, and once during each of 2 phone calls.

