D2.3. Subject identification, recruitment, and randomization: Participants will be recruited from the Denver VAMC, UCHealth Highlands Ranch, and UCHealth Broomfield. Two hundred and fifty Veterans will be recruited (3-4 patients per month) with at least 112 expected to complete through the 60 day episode of care to accommodate for the potential re-hospitalization rate of 20-30% among home care recipients³² and drop-outs for other reasons. We had no difficulty recruiting patients for our preliminary study (3-4 patients/month). The Denver VAMC coordinates home health services for approximately 300 Veterans/month. Of these, approximately 30/month would be eligible for this study (> 55 years old; receiving home health PT services for decreased mobility after an acute hospitalization; living within the Denver metropolitan area). Therefore, recruitment of 3-4 patients/month through the Denver VAMC alone should allow us to meet our recruitment goals

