We have established the following apriori stopping criteria for removing a Veteran from the study to maintain the safety of the participant.

Participants will be withdrawn from the study by the investigators if:

a.) They are admitted to the hospital after enrollment and the study physician determines the Veteran unsafe or inappropriate for high intensity rehabilitation as defined by the inclusion/exclusion criteria

b.) They develop a new medical or psychiatric condition after enrollment which precludes participation in exercise training based on ACSM criteria or the determination of a physician, safety officer, or investigator (i.e. new cardiac diagnosis such as unstable angina, marked change in cognition, acute illness, pneumonia)

Expected Adverse and Serious Adverse Events:

The following are expected AEs and SAEs for this study: High risk behavior, e.g. drug use and/or alcohol abuse; hospitalizations due to poor functional mobility, e.g. falls; and complication from or exacerbation of current medical diagnoses and comorbidities.

Data Management Risks: As with any study, there is a risk of data breach or disclosure of study data outside the study team (e.g through accidental loss of data, theft, inadvertent electronic or paper disclosures). We will minimize these risks through the following protocol for collecting data:

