Missing Data. All patients with outcome measurements will be included in the intent-to-treat analysis. Although we will encourage patients to be fully compliant to their assigned treatment regimen and testing sessions, they will not be dropped from follow-up measurements for lack of compliance. Although statistical methods can be used to "adjust" for missing data, these methods rely on the untestable assumption that data are "missing at random" so that the effect of the missingness can be removed through statistical modeling. We will instead focus on preventing missed follow-up visits and evaluate missingness to determine whether the data are consistent with the hypothesis of missing at random or missing completely at random.

F. Data Analysis Plan:

Primary and Secondary Outcomes: The primary outcome for this study is gait speed measured 60 days following hospital discharge. Secondary outcome measures include SPPB measured at other study time points, mPPT, LSA, NEADL, VR-12, and CBI, measured at designated study time points (see Table 3). The 60 day time point is chosen for clinical relevance because it helps establish not only efficacy but also sustainability of the effects after the initial 30-day intervention period. Preliminary descriptive and graphical analyses (including boxplots, scatterplots, profile plots) will be used for data cleaning and visualization.

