Enrollment in the study will be defined as participating in the baseline functional performance measures. We expect to enroll 150 Veterans and spouses into the study, with 112 needed to complete to meet study goals. From our experiences and available data, we anticipate a 25% drop out. Caregivers will be consented after a Veteran or spouse is enrolled in the study, thus we anticipate enrolling 150 caregivers. Caregivers will undergo assessment of caregiver burden on the outcome measurement schedule above until the conclusion of the 180 day study period, or until the Veteran or spouse for whom they give care is lost to the study (e.g re-hospitalized)— similarly, we anticipate to need 112 to complete.

Thus, in total, we anticipate consenting 250 Veterans and spouses for the study, enrolling 150 of them, and expecting 112 to complete. We will additionally be consenting 150 caregivers with 112 expecting to complete. For the total study, we will be consenting 400 participants (250 Veterans and spouses, 150 caregivers) and expecting 224 to complete (112 Veterans and spouses, 112 Caregivers). These numbers have been provided to as part of the grant application process to the Veterans Administration Rehabilitation Research and Development Service and were favorably reviewed and pending a funding announcement for a Merit Award (R01 equivalent).

G. Summarize Knowledge to be Gained:

There is a growing recognition that acute hospitalization contributes to long-term disability for hospitalized older adults—who are 60 times more likely to develop disability than those who are not hospitalized. Older Veterans are particularly vulnerable to functional decline after

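### Caregiver-burden follow-up ends when the Veteran is lost to the study, with re-hospitalisation as the example; this cuts off Aim 3 data after an event that may be related to burden and to arm, and conflicts with the withdrawal criteria

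*Combined protocol and SAP*

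**What the plan says.** - **CBI schedule.** Hypothesis 3.1 (Specific Aim 3) sets the times for quality of life, cognition and caregiver burden: "Assessments will occur at baseline, 60, and 180 days". Table 1 shows the same three CBI visits.
- **Caregiver stopping rule.** Under F. Data Analysis Plan, Sample Size Estimates, caregivers are assessed to day 180 "or until the Veteran or spouse for whom they give care is lost to the study (e.g re-hospitalized".
- **Recruitment (D2.3).** The gap between Veterans recruited and Veterans completing is there "to accommodate for the potential re-hospitalization rate of 20-30% among home care recipients", along with other drop-out. Re-hospitalisation is thus counted as attrition.
- **Veteran withdrawal (section C, stopping criteria).** The investigators withdraw a Veteran if "They are admitted to the hospital after enrollment and the study physician determines the Veteran unsafe or inappropriate for high intensity rehabilitation". Two conditions are needed, the admission and the physician's judgement.
- **Continued follow-up.** The Missing Data paragraph says of participants that "they will not be dropped from follow-up measurements for lack of compliance". The adverse-event script, given at each study visit and in two phone calls, asks about events ("e.g. ER visit(s), hospitalization(s), major illness/injury) which occurred since the last study visit").
- **Missing data.** The same paragraph declines statistical adjustment. It relies on preventing missed visits and on examining the pattern of missingness.

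**The concern.** Two problems sit in the one clause.

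First, the sections disagree on what an admission does. If the example in the caregiver clause is taken at face value, re-hospitalisation alone is loss to the study. Under the section C criteria it is not. Consider a Veteran readmitted on day 20, discharged on day 24 and not withdrawn. That Veteran is tested at days 60, 90 and 180. On the face-value reading, the caregiver gives no CBI after baseline.

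Second, and whichever reading is right, the clause ends the collection of a caregiver's own questionnaire because of something that happened to the Veteran after randomisation. That event is plausibly related to the outcome: section B.3 argues that "one of the strongest predictors of high caregiving burden is the functional ability of the Veteran being cared for", and section B.1 ties poor function to readmission risk. It may also be related to arm, since PHIT aims to raise function and the plan itself compares re-hospitalisation rates between arms.

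What is at stake is the Aim 3 caregiver comparison. With selective loss it describes families whose Veteran was not re-hospitalised or lost, which is narrower than the population of Hypothesis 3.1. A caregiver stopped before day 60 has only a baseline value and contributes nothing to the 60-day change regression.

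**Working it through.** **1. The plan's own numbers.** Inputs from Sample Size Estimates: gait-speed difference 0.18 m/s, SD 0.29 m/s, two-sided alpha 0.05, power 90%.

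- n per arm = 2 x (1.960 + 1.282)^2 x (0.29/0.18)^2 = 54.5, so 55. At the stated 56 per arm, t-test power is 90.2%.
- 150 x (1 - 0.25) = 112.5, which matches 112 completers.

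These figures reproduce. The 150 and 112 were derived for gait speed and carried over to caregivers. No separate power calculation is given for the CBI.

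**2. How many caregivers could be affected.** Inputs: 150 caregivers (Sample Size Estimates) and 20-30% re-hospitalisation (D2.3, one overall rate, none by arm).

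- 0.20 x 150 = 30 and 0.30 x 150 = 45. This is an upper bound at that rate, because it assumes that every re-hospitalisation ends caregiver follow-up.
- If the rate covers all 180 days, fewer are affected at day 60: anyone first readmitted later has already given that CBI. D2.3 mentions the rate alongside the 60-day episode but does not state its time window. If it covers only 60 days, the day-180 count could be higher.
- Caregivers stopped while their Veteran is still followed: the documents do not say what share of re-hospitalised Veterans remain. Assuming 25-75%, the range is 150 x 0.20 x 0.25 = 7.5 to 150 x 0.30 x 0.75 = 33.75, or about 8 to 34. If the clause means only Veterans admitted and withdrawn, this number is zero.

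**3. What the pilots show by arm.** D1.4 reports that "PHIT group participants had no ER visits or re-hospitalization at 90 days, while 6 episodes (over 2 individuals") occurred in usual care (UC). Sample Size Estimates gives the arm sizes as 8 PHIT and 10 UC.

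- 0/8 versus 2/10 individuals: Fisher exact p = 0.48; exact 95% intervals 0-37% and 2.5-56%. The count pools emergency visits with re-hospitalisations.
- The feasibility study in D1.3 (10 patients) reports 3 re-hospitalisations and 1 emergency visit in UC against 1 emergency visit in PHIT. These are episodes, without arm sizes.

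Both lean the same way. Neither establishes a difference.

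**4. Possible size of the bias.** Let p be the share of families dropped after re-hospitalisation. Let D be their excess burden, in SD units, not explained by baseline CBI. If D is the same in both arms, dropping these families removes (p_UC - p_PHIT) x D from the UC-minus-PHIT difference. All rates and values of D below are assumptions.

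| UC rate | PHIT rate | Removed, D = 0.25 to 1.0 SD |
|---|---|---|
| 25% | 25% | 0 |
| 30% | 20% | 0.10 x D = 0.025 to 0.10 SD |
| 30% | 10% | 0.20 x D = 0.05 to 0.20 SD |
| 20% | 0% | 0.20 x D = 0.05 to 0.20 SD |

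With D = 0 the term is zero at any rates. If PHIT had more readmissions, the sign would reverse and the loss would favour PHIT. If D differed by arm, the term would be p_UC x D_UC - p_PHIT x D_PHIT, which need not be zero at equal rates.

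For scale, 56 per arm has 90% power for (1.960 + 1.282) x sqrt(2/56) = 0.61 SD.

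**The case against.** The best defence is textual. The written trigger is loss to the study, and re-hospitalisation is only an example. Read with section C, the example may mean a Veteran admitted and then withdrawn, so that caregiver and Veteran stop together. The clause also sits in a sample-size narrative, while Hypothesis 3.1 and Table 1 set the CBI visits with no stop. This stands: a reader might infer that the plan definitely stops caregivers of Veterans who remain in the trial, but the text is ambiguous and does not establish that. It does not remove the second problem. The section C criteria concern the Veteran's fitness for high-intensity rehabilitation, which is no reason to stop a questionnaire answered by a separately consented caregiver.

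Three other objections also limit the point.

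- **Arm difference.** A reader might infer that readmission is expected to be lower with PHIT. Hypothesis 1.1 claims only no increase in adverse events. The Summary after section B.5 mentions possible reductions in health care utilisation as a potential benefit, and the pilots are too small to settle it.
- **Size.** The excess-burden values are assumed, and adjustment for baseline CBI would absorb part of any excess already present at entry. A 25% loss is already planned, so lower precision from a loss of that size is not an added cost.
- **Main conclusion.** A reader might infer that a masked CBI effect would undermine the trial's main result. Statistical significance rests on one gait-speed test. The CBI is one of ten other listed outcomes in a qualitative consistency check.

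There is also a practical reason behind the clause: caregivers are eligible through an enrolled participant and are consented in that participant's home. That explains the rule, but it does not prevent phone or mail collection.

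**Conclusion.** The point holds as a wording conflict plus an avoidable source of informative loss in a secondary outcome. The caregiver clause and D2.3 treat re-hospitalisation as loss, while section C does so only with a physician's judgement. On either reading, day-60 and day-180 CBI data can be cut off after an event plausibly related to burden and possibly to arm, with no adjustment planned.

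At the plan's 20-30% rate, at most 30 to 45 of 150 caregivers are affected. About 8 to 34 would be stopped while their Veteran is still followed, if 25-75% of re-hospitalised Veterans remain (an assumption). The bias is zero if readmission rates and baseline-adjusted excess burden are alike by arm. It is likely modest (0.025 to 0.20 SD in the unequal-rate cases shown) and toward no effect if UC has more readmissions. Neither direction nor size can be fixed from the documents. The sample size and the primary gait-speed test are not affected.

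**What to change.** 1. Reconcile D2.3, the section C withdrawal criteria and the caregiver clause in Sample Size Estimates on whether re-hospitalisation alone counts as loss to the study. Which withdrawal rule is right is for the investigators and is not decided here.
2. Separately, amend the caregiver clause so that consenting caregivers complete the CBI at 60 and 180 days regardless of the Veteran's re-hospitalisation or withdrawal from therapy. Exceptions are that the caregiver withdraws, is no longer the caregiver, or the Veteran dies. Allow phone or mail completion when there is no home visit, and flag any CBI completed during an inpatient stay.

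The cost is a small amendment to the caregiver procedures and a few extra phone or mail questionnaires. Some CBIs will reflect burden during an admission, which is why they need the flag. CBI values not collected at the time cannot be recovered later.
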